6.0 Measurement of Effect

6.1 Antitumor Effect

Response and progression will be evaluated in this study using the new international criteria proposed by the Response Evaluation Criteria in Solid Tumors (RECIST) Committee [JNCI 92(3):205-216, 2000]. The only change from RECIST v.1.1 being implemented in this study is a confirmation of new lesions or progressive disease (PD) by a second scan >6 weeks apart, based on the immune RECIST (ir-RECIST) criteria proposed by Wolchok. *et. al* that is appropriate for immune-related treatment response [89]. This is primarily because immune response often can take longer time as compared to chemotherapy before producing a radiographic response and during this time new lesions may arise which will eventually regress. If it were not for a second confirmation, these patients would be labeled to have failed therapy. Additional criteria for bone lesions and clinical endpoints of pathologic fracture and cord compression are added to this study (see Section 6.1.4). Changes in only the largest diameter (unidimensional measurement) of the tumor lesions are used in the RECIST v1.1 criteria outlined in <http://www.recist.com/>. The primary endpoint will be evaluated using RECIST v1.1 and secondary endpoint will be ir-RECIST.

6.1.1 Definitions

Evaluable for toxicity. All subjects will be evaluable for toxicity from the time of their registration.

Evaluable for objective response. Only those subjects who have undergone SABR and 1 cycle of Nivolumab and have had their disease re-evaluated at least at two occasions will be considered evaluable for response. These subjects will have their response classified according to the definitions stated below.

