4.4 Duration of Follow Up

For patients who respond to treatment, subjects will be followed for five years or until death (although findings will be analyzed and reported at a median follow up of 2-4 years), whichever occurs first. For these patients, follow-up will be every 8 - 12 weeks from study registration with imaging studies and physical exam (recommended) every 8-12 weeks for the first year, then every 8-12 weeks for the second year, then every four-six months thereafter for a total of five years.

Subjects who show progressive disease will be followed for survival and will no longer strictly adhere to study calendar requirements.

Subjects removed from treatment for unacceptable adverse events will be followed until resolution or stabilization of the adverse event.

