5.3 Follow-up Procedures

- For patients who are still receiving Nivolumab:

Subject will be followed every 8-12 weeks starting from the date of registration for the first two years. , then every four-six months thereafter for five years or death, whichever comes first. The following procedures will be performed at each follow up:

- Physical exam (recommended), Performance Status (recommended), Vital Signs, Medication Review, AE assessment
- HR-QoL questionnaire at baseline, and then at six month intervals until patient meets primary endpoint
- Blood collection for correlative immunologic studies (see section 9.0): In total, all patients will get blood draws for correlative studies at baseline, follow up q 8-12 weeks (until discontinued or within first year of enrollment, whichever is first) and at 1 year (if discontinued before 1 year).
- Radiographic imaging: Tumor assessments will be completed by the investigator using the RECIST and ir-RECIST criteria as above.
 - CT chest, abdomen and pelvis with IV contrast (contrast recommended), if allowable by renal function. MRI with contrast (contrast recommended) can replace CT.
 - MRI, if necessary to confirm CT findings, at the discretion of physician

- For patients who have been discontinued from Nivolumab (See Section 4.3): Subject will be followed within 3 months from last dose ((+/- 2 months), or may be on date of discontinuation).

The following procedures will be performed:

- Physical exam (recommended), Performance Status (recommended), Vital Signs, Medication Review, AE sssessment
- Subsequent anti-cancer treatment/s
- Blood samples for correlation immunologic studies

After that, survival visits/phone calls continue annually to include Survival Status, AE Assessment, and Subsequent anti-cancer treatment/s.

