5.4 Time and Events Table

The above recommended labs are listed in the following table but investigators in the various participating institutions may obtain labs per their standard of care to assess suitability for treatment.

	Pre-study	Cycle Day 1 Infusion	Pre-RT	Radiation Treatment	Follow Up Schedule for Patients who respond to treatment (for other patients refer to Section 5.3)		
					Months 1-12: q8-12 Weeks	Months 13-24: q8-12 Weeks	Months 25-60: q16-24 Weeks
Informed Consent	X						
Vital Signs	X	X		X	X	X	X
Medical History	X				X	X	X
Physical Exam (recommended)	X	X			X	X	X
Performance Status (recommended)	X				X	X	X
AE Assessment	X	X		X	X	X	X

Medication Review		X				X	X	X
CT Chest, Abd**, pelvis w/ Contrast	X					X	X	X
MRI Brain w/contrast	X							
Tumor Assessment	X							
Biopsy of metastatic lesion	X^					X@		
CT Simulation			X					
SABR Treatment				X				
Blood Draw for Correlative Studies (Section 9.0)	X#	X#		X#		X#		
QOL Questionnaires	X					X%	X%	X%
Cost-Effectiveness Questionnaire	X					X^^		
Tumor assessment	X							

** MRI should be considered, in place of CT, on an individual basis if felt to be better by the radiation or medical oncologist.

¹ For cycle 1, no need to repeat blood tests at day 1

Immunologic blood collection is needed at baseline, follow up q 8-12 weeks (until discontinued or within first year of enrollment, whichever is first) and at 1 year (if discontinued before 1 year).

^ if previous biopsy of metastatic site with adequate review of slides is not available.

^^ Cost Effectiveness Questionnaire administered at Baseline, 8 week follow up and 6 month follow up.

@ Biopsy is optional at 8 weeks

% QoLs will be done at baseline and then at 6 month intervals

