5.5 Removal of Subjects from Study Treatment or Study

Subjects can be taken off the study treatment and/or study at any time at their own request, or they may be withdrawn at the discretion of the investigator for safety, behavioral or administrative reasons. The reason(s) for discontinuation will be documented and may include:

- 5.5.1 Subject voluntarily withdraws from treatment (follow-up permitted);
- 5.5.2 Subject withdraws consent (termination of treatment and follow-up);
- 5.5.3 Subject is unable to comply with protocol requirements; patients must be withdrawn from the trial and replaced if they failed to receive the SABR treatment. Any patient with at least one cycle of Nivolumab and SABR will be included in the analysis.
- 5.5.4 Subject demonstrates disease progression (unless continued treatment with Nivolumab is deemed appropriate at the discretion of the medical oncologist);
- 5.5.5 Subject experiences toxicity that makes continuation in the protocol unsafe;

- 5.5.6 Treating physician judges' continuation on the study would not be in the subject's best interest;
- 5.5.7 Subject becomes pregnant (pregnancy to be reported along same timelines as a serious adverse event);
- 5.5.8 Development of second malignancy (except for basal cell carcinoma or squamous cell carcinoma of the skin) that requires treatment, which would interfere with this study;
- 5.5.9 Lost to follow-up. If a research subject cannot be located to document survival after a period of 2 years, the subject may be considered "lost to follow-up." All attempts to contact the subject during the two years must be documented .

5.6. Subject Replacement: Subject replacements are allowed in the following situations:

- 5.6.1 If the subjects decide to withdraw from the study without finishing the course of SAbR
- 5.6.2 If the subjects decide to withdraw from the study or lost to follow up (for reasons of death from other causes, moving to other state etc.) or refuse follow up scans leading to <2 follow-up scans (making it impossible to assess the primary endpoint of the trial)

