6.1.4.3 Evaluation of Best Overall Response

The best overall response is the best response recorded from the start of the treatment until disease progression/recurrence (taking as reference for progressive disease the smallest measurements recorded since the treatment started). The subjects' best response assignment will depend on the achievement of both measurement and confirmation criteria.

Target Lesions	Non-Target Lesions	New Lesions	Overall Response	Best Response for this Category Also Requires:
CR	CR	No	CR	≥4 wks. confirmation
CR	Non-CR/Non-PD	No	PR	≥4 wks. confirmation
PR	Non-PD	No	PR	
SD	Non-PD	No	SD	Documented at least once ≥4 wks. from baseline
PD	Any	Yes or No	PD	no prior SD, PR or CR
Any	PD*	Yes or No	PD	
Any	Any	Yes	PD	

* In exceptional circumstances, unequivocal progression in non-target lesions may be accepted as disease progression.
 
Note: Subjects with a global deterioration of health status requiring discontinuation of treatment without objective evidence of disease progression at that time should be reported as “symptomatic deterioration”. Every effort should be made to document the objective progression even after discontinuation of treatment.
				

Note: If subjects respond to treatment and are able to have their disease resected, the patient’s response will be assessed prior to the surgery.

6.1.4.4 Evaluation of Bone Lesions:

Bone lesions will be evaluated either by CT or MRI, whichever is deemed to be better suited by baseline studies. Since the size of the lesion is difficult to measure in a bone scan, particularly if it is not well visible in CT, the following guideline will be used. Any ambiguity will require MRI for resolution:

6.1.4.4.1 Progression of bone lesions will be defined as follows:

- Appearance of 1 or more new bone lesion in CT scan, confirmed by a repeat scan in ≥6 weeks.

6.1.4.4.2 Response of bone lesions in CT scan will be defined by either a complete resolution (CR) at the metastatic sites or partial resolution (PR) of radiotracer uptake by a radiologist.

6.1.4.5 Evaluation of Pathologic Fracture:

Any clinical suspicion of pathologic fracture will prompt radiologic evaluation with plain film, CT or MRI as appropriate and if confirmed by a radiologist, will constitute progression, unless it is at a treated site, in which case a treatment-related toxicity will be considered. In that case, patients will be referred for orthopedics specialist evaluation.

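### The denominator of the primary response rate is not settled, and patients who cannot be assessed are never counted as non-responders; if they respond less often than those kept, the rate is overstated against the fixed 25%

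*Combined protocol and SAP*

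**What the plan says.** - **Response set (6.1.1).** Only patients with SABR, one cycle of nivolumab and who "have had their disease re-evaluated at least at two occasions will be considered evaluable for response" have their response classified.
- **No SABR (5.5.3).** "patients must be withdrawn from the trial and replaced if they failed to receive the SABR treatment".
- **A second inclusion rule (also 5.5.3).** "Any patient with at least one cycle of Nivolumab and SABR will be included in the analysis". It does not say which analysis is meant, or how a patient with one scan or none would be classified.
- **Too few scans (5.6.2).** Replacement is allowed for patients who withdraw, are lost to follow-up, or "refuse follow up scans leading to <2 follow-up scans (making it impossible to assess the primary endpoint of the trial").
- **Scan schedule.** Repeat CT in the 5.4 table falls under a column headed "Follow Up Schedule for Patients who respond to treatment (for other patients refer to Section 5.3"). Section 5.3 lists imaging for patients still on nivolumab. For those who have stopped it lists one visit without imaging, and then "After that, survival visits/phone calls continue annually to include Survival Status, AE Assessment, and Subsequent anti-cancer treatment/s". Section 4.4 adds: "Subjects who show progressive disease will be followed for survival and will no longer strictly adhere to study calendar requirements".
- **Primary test (11.2, 11.3).** An exact binomial test against 25%, with 19 patients for 80% power at 50%, two-sided level 0.2, and accrual of 21 to cover dropouts. Section 11.3 names no analysis population and no rule for patients who cannot be assessed.

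**The concern.** Response rate is the only powered endpoint, and it is compared with a fixed number. No concurrent control arm is subject to the same exclusions. Both conditions for being evaluable, reaching SABR and having two later assessments, can depend on how the patient fares. Follow-up is every 8 to 12 weeks, so two scheduled assessments take about 16 to 24 weeks. The nivolumab median PFS cited in section 1.4.2 is 4 to 4.6 months, or about 17 to 20 weeks (4 × 52/12 = 17.3; 4.6 × 52/12 = 19.9). Patients who die early, stop for toxicity, withdraw, or fall under the 6.1.4.3 note on "Subjects with a global deterioration of health status requiring discontinuation of treatment without objective evidence of disease progression" may have fewer than two assessments.

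If such patients leave the denominator and are replaced, the rate among those who remain is compared with a historical rate that may have counted everyone treated. Separately, because 5.5.3 and 6.1.1 disagree, two analysts could defend different denominators after seeing the data.

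**Working it through.** **Inputs from the plan (11.2):** null rate 0.25, alternative 0.50, n = 19, two-sided level 0.2 (0.10 per tail), accrual 21, so a dropout allowance of 2/21 = 9.5%.

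**Assumptions, not in the documents:** the historical 25% counts all treated patients; the true rate in all treated patients is 25%; excluded patients are replaced so that 19 are analysed. The share excluded, q, and the response rate of the excluded, r, are not given and are varied below.

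**Step 1. Reproduce the plan.** With X binomial(19, 0.25), P(X ≥ 8) = 0.077, and P(X ≥ 7) = 0.175 exceeds 0.10, so the upper cut-off is 8. Power at 0.50 is 0.820. At n = 18 the cut-off is also 8 and power is 0.760. Nineteen is therefore the smallest n reaching 80% at 0.10 per tail, in line with the plan.

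**Step 2. Rate among those kept.** p = (0.25 − q·r)/(1 − q). With r = 0:
- q = 1/21: 0.25 × 21/20 = 26.3%
- q = 2/21: 0.25 × 21/19 = 27.6%

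**Step 3. Chance of rejecting with 19 analysed (r = 0).** The lower-tail cut-off is 1 or fewer.

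| Excluded | Rate among kept | P(≥8 of 19) | P(≤1 of 19) | Total |
|---|---|---|---|---|
| none | 25.0% | 0.077 | 0.031 | 0.108 |
| 1 of 21 | 26.3% | 0.099 | 0.024 | 0.122 |
| 2 of 21 | 27.6% | 0.126 | 0.018 | 0.144 |

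**Step 4. Dependence on r at q = 2/21.** At r = 10%, p = (0.25 − 0.0095)/0.9048 = 26.6% and the upper tail is 0.105. It equals 0.10 at r = 12.4%. At r = 25% there is no bias (0.077).

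**Step 5. Same responders, two denominators.** Eight of 19 gives a doubled-tail p of 2 × 0.0775 = 0.155, significant at 0.2. Eight of 21, with two failures counted, gives 2 × 0.1299 = 0.260, not significant. Exactly eight responders in 19 has probability 0.049 at a 25% rate and 0.144 at 50%, so this reversal is possible but not the usual case.

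**Step 6. Cut-offs for an all-treated denominator (upper tail at 25%).** ≥8/20 is 0.102, just over the limit, so 9 is needed from n = 20: ≥9/20 is 0.041, ≥9/21 is 0.056, ≥9/22 is 0.075 and ≥9/23 is 0.096.

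**The case against.** The strongest reply is that 5.5.3 keeps treated patients with fewer than two re-evaluations. A reader might infer that all such patients are certain to leave the primary rate. The documents do not support that: 5.5.3 and 6.1.1 contradict each other for this group. Only the removal of patients without SABR is common to both.

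A reader might also infer that early progressors drop out wholesale. That goes too far. Under section 4.2.1.1, progression on a first set of scans should be verified on a second before treatment is stopped, and treatment beyond progression is permitted. The 6.1.4.3 note on deterioration asks for every effort to document objective progression after treatment ends. These provisions keep some early failures in. Section 5.6.2 gives death from other causes as an example of replaceable loss; it does not list death from renal cancer, so the assumption that every excluded patient is replaced is a worst case.

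Excluded patients need not all be non-responders either, since the 6.1.4.3 table asks for no confirmation when target lesions show PR, so one scan can establish a response.

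Finally, the trial asks what SABR adds, so a denominator that includes patients never given SABR is open to debate. That stands as a reason to report both sets. What survives all of this is that no primary set is named, two sections disagree, and no rule treats unassessable patients as failures.

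**Conclusion.** The concern holds in conditional form. That the denominator is undefined and internally inconsistent is clear from the text and needs no assumption. That the response rate is biased upward depends on excluded patients responding less often than those kept, and on the historical 25% counting all treated patients; the documents establish neither.

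At the plan's own allowance the worst case is 2.6 percentage points (27.6% against 25%) and an upper tail of 0.126 against 0.10. With one patient excluded the upper tail is 0.099, still within the limit. It would be wrong to infer that the stated two-sided level of 0.2 is breached: total rejection reaches only 0.144 in that worst case. The matter should be fixed before the data are analysed, but it does not invalidate the design.

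**What to change.** 1. Reconcile 5.5.3, 5.6 and 6.1.1, and say which analysis the inclusion sentence in 5.5.3 refers to.
2. In 11.3, define the primary response-rate denominator as all registered patients who start study treatment, including any who are replaced. Count anyone without a documented RECIST 1.1 response as a non-responder, whatever the number of scans.
3. State the cut-off by number analysed at 0.10 per tail: at least 8 for n = 19, at least 9 for n = 20 to 23.
4. Report the set with SABR and two re-evaluations as a sensitivity analysis, and list separately any response in a patient who never had SABR, because it would otherwise count as a success of the combination.

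**Cost.** The change is to wording and needs no additional scans or enrolment. The reported rate will be less favourable, and the power statement must be revised. At a 50% rate, ≥9/21 has power 0.808 with no failures, 0.748 with one forced non-responder (at least 9 of the other 20) and 0.676 with two (at least 9 of the other 19). For ≥9/20 it is 0.748 with none. Where these fall below the planned 80%, the protocol should say so.

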6.1.2 Disease Parameters

Measurable disease. Measurable lesions are defined as those that can be accurately measured in at least one dimension (longest diameter to be recorded)

as ≥ 10 mm with spiral (Helical) CT scan (CT/MRI scan slice thickness should be no greater than 5 mm). All tumor measurements must be recorded in millimeters (or decimal fractions of centimeters). For malignant lymph nodes to be considered pathologically enlarged and measurable, a lymph node must be ≥ 15 mm in short axis when assessed by CT scan (CT scan slice thickness recommended to be no greater than 5 mm). At baseline and in follow-up, only the short axis will be measured and followed. Bone scan, PET scan or plain films are not considered adequate imaging techniques to measure bone lesions. However, these techniques can be used to confirm the presence or disappearance of bone lesions. Lytic bone lesions or mixed lytic-blastic lesions, with identifiable soft tissue components, that can be evaluated by cross sectional imaging techniques such as CT or MRI can be considered as measurable lesions if the soft tissue component meets the definition of measurability described above.

Non-measurable disease. All other lesions (or sites of disease), including small lesions (longest diameter < 20 mm with conventional techniques or < 10 mm using spiral CT scan) and lymph nodes < 15 mm, are considered non-measurable disease. Leptomeningeal disease (patients excluded), ascites, pleural/pericardial effusions, lymphangitis cutis/pulmonis, inflammatory breast disease, abdominal masses (not followed by CT or MRI), and cystic lesions are all non-measurable. Blastic bone lesions are non-measurable. Lesions that meet the criteria for radiographically defined simple cysts should not be considered as malignant lesions (neither measurable nor non-measurable) since they are, by definition, simple cysts. 'Cystic lesions' thought to represent cystic metastases can be considered as measurable lesions, if they meet the definition of measurability described above. However, if non-cystic lesions are present in the same subject, these are preferred for selection as target lesions.

Target lesions. All measurable lesions up to a maximum of 2 lesions per organ and 5 lesions in total, representative of all involved organs, should be identified as **target lesions** and recorded and measured at baseline. Target lesions should be selected on the basis of their size (lesions with the longest diameter) and their suitability for accurate repeated measurements (either by imaging techniques or clinically). A sum of the longest diameter (LD) (longest for non-nodal lesions, short axis for nodal lesions) for all target lesions will be calculated and reported as the baseline sum LD. The baseline sum LD will be used as reference by which to characterize the objective tumor response.

Note: Lesions receiving SABR will be called "radiated lesion" which should not be confused with "target lesions" defined here for the for the purpose of radiographic measurement. Radiated lesions and target lesions are mutually exclusive lesions. Therefore, radiated lesions will not be used as target lesions for evaluating response. At least 2 non-CNS measurable lesions are required for enrollment.

Non-target lesions. All other lesions (or sites of disease) including any measurable lesions over and above the 6 target lesions should be identified as **non-target lesions** and should also be recorded at baseline. Measurements of these lesions are not required, but the presence or absence of each should be noted throughout follow-up.

6.1.3 Methods for Evaluation of Measurable Disease

All measurements will be done digitally on the PACs system. All baseline evaluations should be performed as closely as possible to the beginning of treatment.

Whenever possible, the same method of assessment and the same technique should be used to characterize each identified and reported lesion at baseline and during follow-up using appropriate radiologic imaging.

MRI Brain, and CT scan or MRI with IV contrast (whenever possible) will be performed at baseline. Since bone scan is not reliable for RCC, it will only be used to evaluate overall response when positive in baseline scan, and any new lesions found on bone scan must be verified with a CT. Bone scans will not be used for measuring lesion size.

Spiral CT and MRI. All CT scans will be Spiral CT and should be performed using a 5 mm contiguous reconstruction algorithm.

6.1.4 Response Criteria

6.1.4.1 Evaluation of Target Lesions

Complete Response (CR): Disappearance of all target lesions, determined by two separate observations conducted no less than 4 weeks apart. Any pathological lymph nodes must have reduction in short axis to < 10 mm. There can be no appearance of new lesions.

Partial Response (PR): At least a 30% decrease in the sum of the longest diameter (LD) of target lesions, taking as reference the baseline sum LD. There can be no appearance of new lesions.

Progressive Disease (PD): At least a 20% increase in the sum of the LD of target lesions, taking as reference the smallest sum LD recorded since the treatment started, or the appearance of one or more new lesions verified by a second scan > 6 weeks apart. In addition to the relative increase of 20%, the sum must also demonstrate an absolute increase of at least 5 mm.

Stable Disease (SD): Neither sufficient shrinkage to qualify for PR nor sufficient increase to qualify for PD, taking as reference the smallest sum LD since the treatment started.

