Treatment with immunotherapies has been reported to cause a “tumor flare” which denotes the apparent radiographic increase in tumor burden or occurrence of new lesions before a true clinical response can be established. This “flare” is thought to be due to a transient increase in immune cell infiltration while the immune system is being primed. Therefore, RECIST criteria may fail to accurately report RR and some patients will be taken off therapy before a true response is measured. In the CheckMate 025 trial, 44% of patients who progressed per RECIST criteria were continued on Nivolumab if they were thought to have clinical benefit. In addition, in the phase II trial of Nivolumab dose escalation trial, treatment beyond first RECIST-criteria progression was allowed in patients who tolerated Nivolumab and exhibited investigator-assessed clinical benefit. 17%, 22% and 26% of patients in the 0.3, 2 and 10 mg/kg groups were treated beyond progression. Median number of doses received after RECIST progression was 4.5, 7.5 and 8.5 in the 0.3, 2 and 10 mg/kg groups. Median PFS was 2.7 mos, 4.0 mos and 4.2 mos in the 0.3, 2 and 10 mg/kg groups using the RECIST criteria but increased to 4.3, 5.4 and 6.9 mos respectively using immune-response PFS. In a subgroup analysis, 69% (25/36) of patients who received treatment beyond first progression, defined as patients receiving their last Nivolumab dose >6 weeks after RECIST-defined progression, demonstrated sustained reductions in tumor burden or lesion stabilization with an acceptable safety profile. Median OS for patients treated beyond first progression was 22 mos vs 12 mos for those not treated. Thus, patients will be allowed to stay on Nivolumab after their first RECIST-criteria progression per the treating physician. Data will be evaluated using the RECIST criteria for primary endpoint and ir-RECIST for secondary endpoint.

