2.2 Secondary Objectives

- 2.2.1 RR based on ir-RECIST
- 2.2.2 To evaluate overall survival (OS), which is defined as the time between date of registration and the date of death due to any cause. In analyzing OS, we will take into account the MSKCC prognostic criteria for mRCC and compare our data to historical controls in the appropriate risk category
- 2.2.3 To evaluate progression free survival (PFS), which is defined as the time between date of registration and the first date of documented disease progression or date of death due to any cause
- 2.2.4 To evaluate complete response rate, which is defined as the percentage of patients who show complete response as per ir-RECIST criteria
- 2.2.5 To evaluate time to progression (TTP), which is defined as time between date of registration and date of documented progression.
- 2.2.6 To evaluate median response duration, which is defined as the time between the date a response (CR or PR) was first seen until date of progression
- 2.2.7 To evaluate the tolerability and toxicity as measured according to CTCAE v4.0.
- 2.2.8 To measure the improvement in health-related quality of life (HR-QoL)

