6.1.4.2 Evaluation of Non-Target Lesions

Complete Response (CR): Disappearance of all non-target lesions and normalization of tumor marker level. All lymph nodes must be non-pathological in size (< 10 mm short axis).

Incomplete Response/Stable Disease (SD): Persistence of one or more non-target lesion(s) and/or maintenance of tumor marker level above the normal limits.

Progressive Disease (PD): Appearance of one or more new lesions and/or unequivocal progression of existing non-target lesions

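### For the ir-RECIST response and CR rates, section 6.1.4 contradicts the protocol's own rule that a new lesion counts only once a second scan verifies it

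*Combined protocol and SAP*

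**What the plan says.** Section 6.1 assigns RECIST v1.1 to the primary endpoint and ir-RECIST to the secondary one. It describes the single departure from RECIST v1.1 as second-scan confirmation of new lesions or PD, and gives the reason: "during this time new lesions may arise which will eventually regress". Section 2.1 describes tumor flare in similar terms, as an apparent increase in tumor burden or the "occurrence of new lesions before a true clinical response can be established". Section 2.4.3 requires ir-RECIST progression to be verified by second imaging. Section 4.2.1.1, under continued treatment beyond progression, asks for a second set of scans before a first progression is accepted.

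Two secondary objectives depend on these criteria: 2.2.1, "RR based on ir-RECIST", and 2.2.4, the CR rate by ir-RECIST.

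Section 6.1.4 gives one set of response definitions and does not separate the two criteria:

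- **PD, target lesions (6.1.4.1):** "the appearance of one or more new lesions verified by a second scan > 6 weeks apart".
- **PR (6.1.4.1):** "taking as reference the baseline sum LD. There can be no appearance of new lesions".
- **CR (6.1.4.1):** "Any pathological lymph nodes must have reduction in short axis to < 10 mm. There can be no appearance of new lesions".
- **PD, non-target lesions (6.1.4.2):** "Appearance of one or more new lesions and/or unequivocal progression of existing non-target lesions".
- **Overall table (6.1.4.3):** the last row turns any new lesion into overall PD, whatever the target and non-target status.
- **Best response (6.1.4.3):** "The best overall response is the best response recorded from the start of the treatment until disease progression/recurrence".

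**The concern.** The second-scan requirement reaches the target-lesion PD definition and, in 6.1.4.4.1, new bone lesions. It is missing from PR, CR, non-target PD and the overall table. The patients at risk of misclassification are those section 6.1 describes when it justifies ir-RECIST: a new lesion appears, then goes, and the disease responds.

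At stake are two named secondary endpoints. If 6.1.4 is applied as written, both can be biased downward, and the ir-RECIST rate cannot differ from the RECIST v1.1 rate for this group. Two assessors relying on different sections could also classify the same scans differently, which matters when one patient is a visible share of the sample.

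**Working it through.** **Denominator.** Section 11.2 sizes the trial on the primary response rate: 25% vs 50%, exact binomial test, two-sided 0.2 (0.1 per tail), 80% power, n = 19.

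- Upper rejection at 8 or more of 19: P(X ≥ 8 | 19, 0.25) = 0.0775. Seven would give 0.1749, which is too large.
- Lower rejection at 1 or fewer: P(X ≤ 1 | 19, 0.25) = 0.031. Total error 0.108.
- Power: P(X ≥ 8 | 19, 0.50) = 0.820. At n = 18 it is 0.760.

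The stated n = 19 is reproduced. It rests on the RECIST v1.1 primary endpoint, so nothing below changes it.

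**Test patient.** Scan 1 shows a new lesion. On scan 2, more than 6 weeks later, the lesion is gone, the target sum is at least 30% below baseline and non-target lesions have not progressed.

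| Section | Verification required? | Result for this patient |
|---|---|---|
| 2.4.3, 4.2.1.1, 6.1 | Yes | Not progression; no statement on what PR or CR then requires |
| 6.1.4.1, PD | Yes | Not PD |
| 6.1.4.1, PR and CR | No | Barred from response |
| 6.1.4.2, non-target PD | No | PD at scan 1 |
| 6.1.4.3, last table row | No | Overall PD at scan 1 |
| 6.1.4.3, best response | – | Window closes at that PD |

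1. Under 6.1.4.1 alone, the patient is neither PD nor PR. SD is left by default, although the SD definition speaks only of insufficient shrinkage or growth and does not really fit.
2. Under 6.1.4.2 and 6.1.4.3, the patient is PD at scan 1, and the later shrinkage falls outside the best-response window.
3. On either route the patient is not an ir-RECIST responder. The two routes also contradict each other: the same scan 1 is not PD in 6.1.4.1 and is PD in 6.1.4.2 and 6.1.4.3.

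**Size.** One uncounted responder lowers the ir-RECIST response rate by 1/19 = 5.3 points. If that patient is a complete responder, the CR rate falls by the same amount.

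The documents do not say how often response follows a transient new lesion. As an assumption only, let a share f of all patients be such responders, with a true ir-RECIST rate of 50%. The counted rate is 0.50 − f, the expected loss is 19f, and the chance of losing at least one patient is 1 − (1 − f)^19.

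| f (assumed) | Counted rate | Expected lost of 19 | P(at least one lost) |
|---|---|---|---|
| 0 | 50% | 0 | 0 |
| 0.02 | 48% | 0.38 | 0.319 |
| 0.05 | 45% | 0.95 | 0.623 |
| 0.10 | 40% | 1.90 | 0.865 |

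**The case against.** The best defense is that the protocol, read as a whole, already protects these patients. Section 6.1 introduces the chapter with a study-wide change that names new lesions separately from PD, and 2.4.3 and 4.2.1.1 require verified progression. On that reading an unverified new lesion does not count. The table can also be read scan by scan: at scan 2 the test patient has no new lesion and meets the PR row, and the best-response window is still open because progression was never verified. Finally, ir-RECIST is adopted by citation, and its response rules may come in with it.

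This shows that the intention was probably sound and that exclusion is not certain. It does not remove the contradiction. The general sections say when progression may be declared. None says that an unverified new lesion leaves PR or CR available. The scan-by-scan reading works only if scan 1 is not PD, and 6.1.4.2 and the last table row say that it is. The citation does not settle the matter either, because 6.1.4 writes out its own definitions, and those definitions conflict.

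Two stronger inferences should be resisted. A reader might infer that no flare patient can be counted under ir-RECIST. Section 2.1 also treats transient growth in tumor burden as flare, and a patient with growth alone and no new lesion is not caught by this bar. The two response rates can therefore still differ. A reader might also take the 17% to 26% treated beyond progression in section 2.1 as the size of the affected group. That figure covers everyone treated beyond a first RECIST progression. It is not limited to patients with new lesions, to lesions that vanished or to later responders, so no total bias can be derived from it.

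**Conclusion.** Wrong as written: an internal contradiction affecting two secondary endpoints. For the ir-RECIST response rate and CR rate, 6.1.4 bars response, or declares PD, on an unverified new lesion, while 2.4.3, 4.2.1.1 and 6.1 require verification. Any resulting bias is downward, at 5.3 points per affected patient on a base of 19. The number affected is unknown and may be zero; the rates in the second table are assumptions. The conclusion rests on a literal reading of 6.1.4.1 to 6.1.4.3. A reader who lets the general sections prevail would count the patient, and that possibility of two classifications is why the text should be settled before analysis. The RECIST v1.1 primary endpoint may keep the unqualified bar.

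**What to change.** For the ir-RECIST endpoints only, state that a new lesion counts as PD and bars PR or CR only if verified on a second scan more than 6 weeks later. If it is not verified, response is called on target and non-target lesions and the best-response window stays open. The wording is needed in:

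- 6.1.4.1, the CR and PR definitions;
- 6.1.4.2, non-target PD where a new lesion is the trigger;
- 6.1.4.3, the new-lesion row of the table, and the non-target PD row when only a new lesion triggers it.

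Amending PR and CR alone would not be enough, because 6.1.4.2 would still feed an unverified new lesion into overall PD. Keep the unqualified bar for RECIST v1.1 and say so.

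The cost is a wording amendment and classification of the existing scans under two rule sets. No imaging is added, and the sample size does not change.
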